## **11. Description of the Study Areas/Regions, Design, Materials and Methods:**

***Study Sites.*** Sites engaged in research include the University of Washington, the University of Michigan, Nyanza Reproductive Health Society (NRHS), and the Nyanza, Rift Valley, and Western Kenya LGBTI Network (NYARWEK). Participant recruitment will occur through the NYARWEK Network. Enrollment, all study visits, and clinical care, including PrEP services provided according to the most recent Kenyan Ministry of Health guidelines, will take place in private rooms at the ***Anza Mapema*** Clinic. Intervention delivery will take place at NYARWEK, at private sites used by NYARWEK organizations, or at a meeting space agreed upon and deemed private and safe by both the participant and a ***Shauriana*** peer facilitator trained to deliver the intervention. In-person research team meetings to monitor the study will also be held in private rooms at the ***Anza Mapema*** Clinic, NYARWEK, or at private sites used by NYARWEK organizations. A description of each site's facilities and other resources are included in “Appendix B: Facilities & Other Resources.”

***Study Population.*** The proposed Aim 1 pilot will include 10 adult HIV-negative GBMSM. The proposed Aim 2 intervention trial will include a population of 60 adult HIV-negative GBMSM, all of whom will be recruited in Kisumu, Kenya. The study team and peer facilitators trained to deliver the intervention will also participate in data collection, by providing feedback on intervention feasibility at routine study team meetings that will be minuted.

***Study Design.*** The Aim 1 work will be a prospective pilot of the intervention and of study procedures other than laboratory testing, in a small group of 10 men over a 3-month period, with visits at baseline, month 1, and month 3. During this pilot test, intervention and clinic visit procedures, including data collection tools, will be revised and improved as needed according to feedback on feasibility, comprehension, burden on participants, and acceptability among pilot participants. The Aim 2 work will be an RCT of the final ***Shauriana*** intervention, to test its acceptability, feasibility, and safety and estimate its initial effect size compared to standard care. The final phase of this study will consist of data analysis and dissemination activities.

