***Recruitment.*** Subjects for the Aim 1 Pilot and the Aim 2 intervention trial will be recruited using existing NYARWEK peer networks, snowballing and venue-based referrals. All interested and potentially eligible subjects identified by the NYARWEK team will be given a business card of

the NYARWEK peer facilitator they were in contact with and referred to the *Anza Mapema* clinic for eligibility screening.

Enrolment targets are presented in Table 1. If a participant tests positive for HIV infection at baseline or at any follow-up visit, he will be withdrawn from this study and undergo counselling and referral to the HIV clinic of his choice. Participants who withdraw before or test positive at the month 1 visit will be replaced; replacement participants in the RCT will undergo randomization and not necessarily be assigned to the arm to which the participant they replace was assigned.

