**Table 1. Overview of Participant Enrolment**

Stage	Pilot Test (Aim 1)	Feasibility RCT (Aim 2)
Purpose	Standardization of intervention	Initial testing of feasibility, tolerability, acceptability, and safety; estimate of effect size
Group	10 HIV-negative GBMSM participants	60 HIV-negative GBMSM participants

**Eligibility Screening.** A brief permission script will be used to confirm consent for screening. Basic sociodemographic data (age, sex), a brief risk behavior assessment, and reasons for screening out or failing to enroll will be noted. Men who are found to be ineligible will be referred by *Anza Mapema* staff to HIV prevention or care programming as indicated, including risk reduction counseling, condoms and lubricants, STI screening and treatment, programmatic PrEP if eligible and interested, and HIV care for men who self-report as HIV-positive. Men who are eligible will undergo an informed consent process as described in section 12 (Ethical Considerations).

**Inclusion criteria:** Men recruited for each study aim must meet all of the following criteria:

- Biologically male at birth and identifies as male, according to self-report
- 18 to 35 years of age
- Resident in the Kisumu area for  $\geq 12$  months
- Reports anal intercourse with a man in the past 3 months
- Not currently taking PrEP for HIV prevention in the past 3 months
- Willing to provide complete locator information
- Willing to undergo all study procedures, including HIV testing and counselling
- Not currently participating in any HIV prevention or vaccine study
- Planning to remain in the study area for at least 6 months

*For the pilot study only, men will be required to speak English, in order to expedite the study team's analysis of feedback from these participants in preparation for the RCT. Of note, approximately 50%-60% of young MSM in Kisumu speak English.*

**Exclusion criteria:** Men who meet any of the following criteria will be excluded from this study:

- Unable to understand the study purpose and procedures
- Unwilling to adhere to study procedures

- Currently under the influence of alcohol or drugs
- Prior diagnosis of HIV infection

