reviewed by the team and discussed at weekly meetings. At the conclusion of the pilot study, we will assess whether we need to revise the intervention based on pilot test findings. If this is the case, we will submit revisions to the ethical review board at Maseno University and to the human subjects research committee at the University of Washington for approval.

**Aim 2 Procedures: RCT of the Shauriana Intervention.** Aim 2 work will use an RCT design to test the acceptability, feasibility, and safety of the **Shauriana** Intervention compared to standard care and estimate initial effect size. Acceptability will be assessed using Likert scales in participant ACASI questionnaires and qualitative exit interviews with participants in each study arm. Feasibility will be assessed at regular research team and peer facilitator meetings, which will be minuted. Safety will be assessed through careful monitoring of study participants to identify and report any adverse events. Information on perceived or experienced social harms and benefits will be collected by study staff at all clinic visits and assessed in greater depth in qualitative exit interviews. Additional trial outcomes that will be monitored and reported include screening and enrollment numbers, visit and intervention attendance, overall retention, and self-reported PrEP uptake and adherence. At the end of the trial, urine samples will be tested for tenofovir (TFV) drug levels (see Laboratory details, below). Dried blood spots will also be collected and stored for future testing of TFV-DP and FTC-TP levels, should funding permit.

Recruitment. The **Shauriana** Intervention pilot RCT will enroll 60 HIV-negative men (30 in the intervention and 30 in SOC) and follow participants for 6 months. We will recruit 60 participants over the course of 3 months; this target is realistic, given enrolment of over 160 men in the **Anza Mapema PrEP** cohort within a 2-month period. Potentially eligible participants will be recruited by NYARWEK, then referred to the **Anza Mapema** Clinic for screening and consenting, as described on pp. 11-12.

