Trial enrollment and randomization. Once consent has been given, participants will be randomized to a study arm. The process of randomization to one of two study arms will be explained carefully and reviewed as part of the informed consent process. Computer-generated randomization will be used to assign participants in a 1:1 ratio to the standard care or intervention group, in blocks of 4, to ensure that equal numbers are randomized across arms. Numbered envelopes indicating the assignment will be prepared in and sealed by the UW CFAR Biometrics Core; study staff will not be aware of an individual's condition until the envelope is opened.

Clinic visits. Consistent with the latest Kenyan guidelines, all trial field-test participants will undergo study procedures at baseline, month 1, month 3, and month 6 at the **Anza Mapema** clinic. As for the pilot study, clinic visits will include HIV counselling and testing, screening for STI symptoms, and individual counselling about HIV prevention methods, including standard of care counselling (information, risk reduction, and PrEP counselling). A standardized physical exam will be performed at each visit, and both blood and urine samples will be collected. For participants taking PrEP, medical history will also focus on PrEP side effects and seroconversion symptoms, and PrEP refills will be provided (monthly for the first 3 months then quarterly). After completing these procedures, RCT participants will complete a detailed ACASI described below. Each of the four clinic visits (baseline, month 1, month 3, and month 6) will take from 1.5 to 2 hours; participants will be reimbursed KSh 500 for each clinic visit.

Standard care. All participants will receive standard care at the *Anza Mapema* Clinic, including standard counseling as described above; screening for depressive symptoms and substance use disorder; monthly *Anza Mapema* peer outreach for education and supply of condoms and lubricants; support group meetings; and social events as described above under “Previous Studies and Rationale.” Attendance at *Anza Mapema* support groups and social events by *Shauriana* study participants will be tracked, as will the content of these group and social events during the study period. To ensure fidelity of delivery for each arm, we will review study progress, procedures, and emergent issues at weekly study meetings.

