Clinical outcomes that will be tracked by the Anza Mapema Clinic using existing data collection instruments include visit attendance, attendance at clinic-sponsored support groups or social events, diagnosis and treatment of STI, HIV test results, PrEP refills, and PrEP-related adverse events and their management. Treatment will be provided for STI syndromes and acute illnesses as needed. All non-scheduled clinic visits will be documented. The study team (both clinic staff and intervention facilitators) will refer participants who need services beyond their capacity to mental health, substance use, advocacy, and/or legal services provided locally. All referrals will be documented.

Men who discontinue PrEP will continue follow-up; PEP will be available for men reporting high-risk exposure while not taking PrEP. Men who seroconvert will be withdrawn from the study and linked to HIV care at *Anza Mapema* or at another HIV clinic of their choice. As described above under “Recruitment,” participants who withdraw before or test positive at the month 1 visit will be replaced; replacement participants in the RCT will undergo randomization and not necessarily be assigned to the arm to which the participant they replace was assigned.

Intervention delivery. Participants assigned to the *Shauriana* intervention will be introduced to an assigned peer facilitator on the day of their enrolment visit, after which telephone, SMS, and/or WhatsApp contacts from peers will begin, with in-person meetings per the intervention schedule described above. For the RCT, the intervention has been expanded to include an initial introductory session where peer facilitators spend time getting to know their assigned participants. Therefore, five core intervention sessions and an optional additional session will be delivered. All peer facilitator contacts with participants and all required and optional intervention sessions will be documented. RCT participants will be reimbursed 350 KSh for their transportation after receiving each of the five core *Shauriana* modules, as participants may need to travel to a safe space for intervention delivery to ensure privacy.

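### Does replacing men who leave by month 1, after randomisation, leave the feasibility rates without a usable denominator?

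*Combined protocol and SAP*

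**What the plan says.** Section 11 gives the size of the randomised trial three times. Study Population: "The proposed Aim 2 intervention trial will include a population of 60 adult HIV-negative GBMSM". Table 1: "60 HIV-negative GBMSM participants". Aim 2 Recruitment: the trial "will enroll 60 HIV-negative men (30 in the intervention and 30 in SOC").

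Randomisation comes straight after consent: "Once consent has been given, participants will be randomized to a study arm". Allocation is 1:1, "in blocks of 4, to ensure that equal numbers are randomized across arms".

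The replacement rule appears in the first Recruitment paragraph: "Participants who withdraw before or test positive at the month 1 visit will be replaced; replacement participants in the RCT will undergo randomization". It adds that the new man will "not necessarily be assigned to the arm to which the participant they replace was assigned". The Aim 2 clinic follow-up text repeats it: "participants who withdraw before or test positive at the month 1 visit will be replaced".

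Table 2 places feasibility among the primary outcomes and lists visit attendance and session delivery as part of its content. Section 13 uses the term intent-to-treat once, for the comparison of retention between arms. It gives no analysis set or denominator for attendance or session delivery.

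**The concern.** A man who leaves before month 1 already holds an allocation, so replacing him does not undo his randomisation. With k replacements, 60 + k men have been randomised. The stated 60 then describes only the men who got past month 1, and a 30/30 split is not assured even among them.

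That leaves two candidate denominators for the process measures: everyone randomised, or the 60 who remained. The choice could matter because the replacement window covers most of the intervention. The core sessions are weekly, and the randomised trial adds an introductory one, making five. Men who leave in the first month are those most likely to have missed sessions. Leaving them out would make delivery and attendance look better than they were, in a trial whose main purpose is to judge feasibility.

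**Working it through.** **1. The plan's own figure.** 2 × 30 = 60 = 15 complete blocks of 4, so 60 with 30 per arm is internally consistent. There is no power-based sample size to reproduce: section 11 (Power considerations) says the trial is not powered for the intervention effect, and section 13 attributes the size to time and budget.

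**2. Number randomised.** With k replacements it is 60 + k. The excess exists only if k is at least 1.

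**3. A plausible k.** The plan gives no early-withdrawal rate. Section 8 gives two retention figures from this team's earlier work. Assuming a constant loss rate:

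- 85% retention in the earlier 60-man adherence pilot (assumed to refer to month 6): 1 − 0.85^(1/6) = 0.0267 lost by month 1; × 60 = 1.6 men.
- 83% retention at month 12 in the Kisumu cohort: 1 − 0.83^(1/12) = 0.0154; × 60 = 0.9 men.

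These are overall losses, and the rule replaces men who withdraw, so formal withdrawals could be fewer. Loss concentrated early would give more. The rule also covers HIV-positive tests at month 1. Sixty men followed for one month contribute 60/12 = 5 person-years. At the Kisumu cohort's 2.3 per 100 person-years that is 5 × 0.023 = 0.12 new infections; at the 4.6 seen in its higher-risk subgroup it is 5 × 0.046 = 0.23. This adds well under one man.

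**4. Effect if replaced men were left out.** For session delivery, take an unfavourable case: every leaver is in the intervention arm, men who stay receive 5 of 5 core sessions, and leavers receive s = 0 or 2. Without the leavers, delivery is 100%. With them, for an arm of n randomised men, it is (5(n − k) + ks)/(5n). After 15 full blocks the arm holds 30, and the next k allocations add 0 to k more.

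| k | n | s = 0 | s = 2 |
|---|---|---|---|
| 1 | 30 | 145/150 = 96.7% | 147/150 = 98.0% |
| 1 | 31 | 150/155 = 96.8% | 152/155 = 98.1% |
| 2 | 30 | 140/150 = 93.3% | 144/150 = 96.0% |
| 2 | 31 | 145/155 = 93.5% | 149/155 = 96.1% |
| 2 | 32 | 150/160 = 93.8% | 154/160 = 96.3% |

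The gap is 1.9 to 6.7 points, and smaller if leavers are split between arms.

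For visit attendance over both arms, assume men who stay attend all four visits and leavers attend baseline only: (240 + k)/(4(60 + k)). For k = 1 this is 241/244 = 98.8%; for k = 2 it is 242/248 = 97.6%. The gap is 1.2 to 2.4 points.

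**5. Does the plan point to leaving them out?** The relevant text, side by side:

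- No sentence excludes a replaced man from any analysis.
- Retention is analysed by intent-to-treat, which in its usual sense counts every randomised man, replaced or not.
- Replacements are freshly randomised and not slotted into the leaver's arm, so they extend the allocation list and do not overwrite an entry.
- Section 11 (Intervention delivery) has all peer contacts and all sessions documented, so the data for leavers exist.
- Section 11 (Aim 2 Procedures) has enrolment numbers, attendance and overall retention reported.
- Early leavers are followed up: an exit interview at withdrawal (section 11, Exit interviews; section 12) and a withdrawal survey asking the reason (section 12, Adequacy of Protection from Risks).
- In the team's earlier pilot (section 8), 24 successful peer pairings are reported as 89%. That is 24/27 = 88.9%, with all 27 men assigned to the intervention in the denominator, including the three who left the peer component.

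**6. Does anything in the plan depend on the answer?** Section 11 calls the Table 1 numbers enrolment targets and states the replacement rule in the same paragraph. The rank and chi-square tests in section 13 do not need equal arms. No feasibility threshold is set, and feasibility is also judged from team meetings and their minutes. The primary quantitative analyses cover acceptability scores and a tally of social harms, not a feasibility rate.

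**The case for a change.** The best case for a change is that the gap sits in a primary outcome of a feasibility trial, where early withdrawal from the intervention is itself a result. Fixing the denominator before the data are seen would stop the same records being reported two ways. It would take two or three sentences and no new data. One further detail is open: some men are withdrawn by protocol after an HIV-positive test, and the plan does not say how visits and sessions due after that point are counted. Larger assumed early losses widen the gap. If 27 men complete all core sessions, that is 27/30 = 90.0%, against 27/33 = 81.8% when three more randomised men are counted.

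The textual facts in this argument stand: more than 60 may be randomised, and the denominator is unwritten. The consequence does not follow from them. The overstatement needs an exclusion that the plan never makes. The 27-of-30 example and the higher loss rates are assumptions with no basis in the documents. Early dropout would remain visible in the intent-to-treat retention comparison, the enrolment counts and the withdrawal records, whichever denominator were used for sessions. The counting of visits after an HIV-positive withdrawal is a reporting convention affecting, on the figures above, a fraction of one man by month 1.

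**Conclusion.** The concern does not call for a change. The plan leaves a detail unstated, but no rule in it gives a wrong result. The numbers 60 and 30/30 are targets with replacement openly disclosed, and fresh randomisation of replacements does not bias the comparison when all randomised men are kept. The text and the team's own earlier practice lean towards keeping them, and the effect is then zero. If replaced men were nevertheless dropped, 1 to 2 leavers would move session delivery by about 2 to 7 points in an unfavourable case and visit attendance by about 1 to 2 points. That size rests on constant loss over time, on reading 85% as month 6 retention, on full attendance by men who stay and, for session delivery, on all leavers being in the intervention arm. No threshold, test or power statement in the plan turns on a difference of that size.

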**Table 1. Overview of Participant Enrolment**

Stage	Pilot Test (Aim 1)	Feasibility RCT (Aim 2)
Purpose	Standardization of intervention	Initial testing of feasibility, tolerability, acceptability, and safety; estimate of effect size
Group	10 HIV-negative GBMSM participants	60 HIV-negative GBMSM participants

**Eligibility Screening.** A brief permission script will be used to confirm consent for screening. Basic sociodemographic data (age, sex), a brief risk behavior assessment, and reasons for screening out or failing to enroll will be noted. Men who are found to be ineligible will be referred by *Anza Mapema* staff to HIV prevention or care programming as indicated, including risk reduction counseling, condoms and lubricants, STI screening and treatment, programmatic PrEP if eligible and interested, and HIV care for men who self-report as HIV-positive. Men who are eligible will undergo an informed consent process as described in section 12 (Ethical Considerations).

**Inclusion criteria:** Men recruited for each study aim must meet all of the following criteria:

- Biologically male at birth and identifies as male, according to self-report
- 18 to 35 years of age
- Resident in the Kisumu area for  $\geq 12$  months
- Reports anal intercourse with a man in the past 3 months
- Not currently taking PrEP for HIV prevention in the past 3 months
- Willing to provide complete locator information
- Willing to undergo all study procedures, including HIV testing and counselling
- Not currently participating in any HIV prevention or vaccine study
- Planning to remain in the study area for at least 6 months

*For the pilot study only, men will be required to speak English, in order to expedite the study team's analysis of feedback from these participants in preparation for the RCT. Of note, approximately 50%-60% of young MSM in Kisumu speak English.*

**Exclusion criteria:** Men who meet any of the following criteria will be excluded from this study:

- Unable to understand the study purpose and procedures
- Unwilling to adhere to study procedures

- Currently under the influence of alcohol or drugs
- Prior diagnosis of HIV infection

Men who screen out or decline enrolment will be reimbursed KSh 350 for transportation to the clinic. Locator information will be collected from all enrolled participants to ensure they can be traced in the event of a missed visit or lab result needing action. In addition, the Anza Mapema clinic provides the option for participants to use iris scanning rather than a study card with their ID number as a means of identification when they present to the clinic. This biometric identification method has been found to be more acceptable to the target population than fingerprint scanning, and helps avoid duplicate enrolments across studies. For study forms that include the recruitment script and eligibility screener and checklist please see "[Appendix C: Eligibility Screener and Checklist.](#)"

***Aim 1 Procedures: Piloting and Standardization of the Shauriana Intervention.*** The overall objective of this phase is to pilot test and standardize our empirically-based, targeted sexual health intervention for Kenyan GBMSM at risk for acquiring HIV. Objectives of the pilot test phase will be to a) assess acceptability of intervention components to the target population; b) test the adequacy of intervention materials and research instruments; and c) monitor fidelity of provider implementation. We will recruit 10 HIV-negative, PrEP-naïve GBMSM who are willing to undergo all intervention procedures at a scheduled roll-out date and provide detailed feedback after each intervention session. Recruitment will be achieved through outreach by the NYARWEK team, with screening and enrolment at the *Anza Mapema* clinic as described above.

Clinic visits. The 10 field-test participants will undergo all study procedures at baseline, month 1, and month 3 at the *Anza Mapema* clinic as detailed below for the aim 2 work. The exception will be specimen collection and laboratory testing, which are currently not included as part of standard of care in Kenyan PrEP programs. Clinic visits will include HIV counselling and testing, screening for STI symptoms, and individual counselling about HIV prevention methods. Standard of care counselling for HIV prevention in Kenya includes general information about HIV transmission and discussions of risk reduction including condom use. PrEP counselling sessions focus on PrEP knowledge, adherence tips, and strategies to address adherence barriers. Our intervention will include this component as standard care at the *Anza Mapema* Clinic. After receipt of these services, pilot study participants will complete the detailed ACASI described below for Aim 2, allowing us to identify any technical problems with this data capture and the questions included. Each of the three clinic visits (baseline, month 1, and month 3) will take from 1.5 to 2 hours; participants will be reimbursed KSh 500 for each clinic visit.

Intervention procedures. In addition to this standard of care, men in the pilot study will receive the *Shauriana* intervention, which is aimed at promoting sexual health and preventing HIV through a comprehensive prevention toolbox including PrEP. The intervention is adapted to respond to the particular needs of Kenyan GBMSM, as identified in the qualitative research conducted in as protocol MSU/DRPI/MUERC/00637/18. The components of this intervention are: four weekly in-person sessions with a trained peer intervention specialist; optional additional in-person or by phone check-ins after the in-person sessions are delivered; and optional monthly group sessions at NYARWEK. The four in-person health education and coaching sessions will be delivered once per week, by trained peer facilitators who identify as GBMSM. These sessions

will focus on the following topics: sexual health basics (understanding how HIV and STIs are transmitted, prevented, and diagnosed/treated), relationships (types of relationships we have, characteristics of healthy relationships, communication skills), stress and coping (understanding mental health challenges, adaptive and maladaptive coping strategies), and healthy sexuality and empowerment (understanding sexual orientation and gender identity, challenging stereotypes about GBMSM, making sexual choices).

An overview of session content is included in "[Appendix D: Shauriana Intervention Draft](#)." Peer facilitators will use a structured counselling format to help participants set specific goals, identify facilitators and barriers, and problem-solve to overcome barriers they anticipate or encounter. One-on-one sessions with peer facilitators will be structured as follows: 15 minutes introduction or review from previous week; 30 minutes didactic sharing of health information; 45 minutes of integrated next step counselling (iNSC) related to the current topic and sexual health. Peer facilitators will document each module administration, which will also be digitally recorded, in order to monitor fidelity of intervention delivery. In addition, participants will be asked to provide both quantitative (i.e., scales) and qualitative (i.e., open-ended questions) feedback on each intervention session delivered. Each session will take from 1.5 to 2 hours; participants will be reimbursed KSh 500 for their time.

A training manual is being designed for the six peer facilitators who will deliver the intervention. This manual will include the didactics and background information necessary to teach the peers the rationale and procedures of the intervention. Training components will be illustrated using role-play exercises, discussion of sample cases, and hypothetical problem scenarios. Peer training will be carried out over 3-4 days at least one week prior to the pilot test, and will include an overview of the study design, theoretical principles, and rationale, as well as step-by-step review of supporting manuals and handouts, practice role-playing exercises, and feedback. Practice sessions will be role-played until each intervention is adequately delivered, as assessed by the research team. We will hold weekly peer facilitator meetings to review study progress, guidelines, and issues that have arisen. Minutes of these meetings will be used to monitor the study and identify needs for revised training or procedures.

Optional intervention components. Once participants have completed the four weekly sessions, peer facilitators will send regular messages to participants to check in with them. If participants choose, they may continue to meet with their peer facilitator for additional iNSC sessions by phone or in-person (this is an optional component of the intervention). Participants may also choose to attend group sessions focused on LGBTI mental health and wellbeing that will be held at NYARWEK (also an optional component of the intervention).

Exit interviews. On completion of each pilot participants' 3 months of follow-up, an in-depth exit interview will be conducted for feedback regarding intervention components and overall study experiences, including any social harms (i.e., inadvertent disclosure, breach of confidentiality) of participation. Participants will be reimbursed KSh 500 for the exit interview. The topic guide for the exit interviews is included in "[Appendix E: Shauriana Exit Interview Guide](#)."

Pilot data analysis. Data from the pilot study will be reviewed on a weekly basis and corrections to ACASI skip rules or other data programming problems will be made immediately. Feedback from participants after intervention sessions and notes taken during interviews will be

reviewed by the team and discussed at weekly meetings. At the conclusion of the pilot study, we will assess whether we need to revise the intervention based on pilot test findings. If this is the case, we will submit revisions to the ethical review board at Maseno University and to the human subjects research committee at the University of Washington for approval.

**Aim 2 Procedures: RCT of the Shauriana Intervention.** Aim 2 work will use an RCT design to test the acceptability, feasibility, and safety of the **Shauriana** Intervention compared to standard care and estimate initial effect size. Acceptability will be assessed using Likert scales in participant ACASI questionnaires and qualitative exit interviews with participants in each study arm. Feasibility will be assessed at regular research team and peer facilitator meetings, which will be minuted. Safety will be assessed through careful monitoring of study participants to identify and report any adverse events. Information on perceived or experienced social harms and benefits will be collected by study staff at all clinic visits and assessed in greater depth in qualitative exit interviews. Additional trial outcomes that will be monitored and reported include screening and enrollment numbers, visit and intervention attendance, overall retention, and self-reported PrEP uptake and adherence. At the end of the trial, urine samples will be tested for tenofovir (TFV) drug levels (see Laboratory details, below). Dried blood spots will also be collected and stored for future testing of TFV-DP and FTC-TP levels, should funding permit.

Recruitment. The **Shauriana** Intervention pilot RCT will enroll 60 HIV-negative men (30 in the intervention and 30 in SOC) and follow participants for 6 months. We will recruit 60 participants over the course of 3 months; this target is realistic, given enrolment of over 160 men in the **Anza Mapema PrEP** cohort within a 2-month period. Potentially eligible participants will be recruited by NYARWEK, then referred to the **Anza Mapema** Clinic for screening and consenting, as described on pp. 11-12.

Trial enrollment and randomization. Once consent has been given, participants will be randomized to a study arm. The process of randomization to one of two study arms will be explained carefully and reviewed as part of the informed consent process. Computer-generated randomization will be used to assign participants in a 1:1 ratio to the standard care or intervention group, in blocks of 4, to ensure that equal numbers are randomized across arms. Numbered envelopes indicating the assignment will be prepared in and sealed by the UW CFAR Biometrics Core; study staff will not be aware of an individual's condition until the envelope is opened.

Clinic visits. Consistent with the latest Kenyan guidelines, all trial field-test participants will undergo study procedures at baseline, month 1, month 3, and month 6 at the **Anza Mapema** clinic. As for the pilot study, clinic visits will include HIV counselling and testing, screening for STI symptoms, and individual counselling about HIV prevention methods, including standard of care counselling (information, risk reduction, and PrEP counselling). A standardized physical exam will be performed at each visit, and both blood and urine samples will be collected. For participants taking PrEP, medical history will also focus on PrEP side effects and seroconversion symptoms, and PrEP refills will be provided (monthly for the first 3 months then quarterly). After completing these procedures, RCT participants will complete a detailed ACASI described below. Each of the four clinic visits (baseline, month 1, month 3, and month 6) will take from 1.5 to 2 hours; participants will be reimbursed KSh 500 for each clinic visit.

Standard care. All participants will receive standard care at the *Anza Mapema* Clinic, including standard counseling as described above; screening for depressive symptoms and substance use disorder; monthly *Anza Mapema* peer outreach for education and supply of condoms and lubricants; support group meetings; and social events as described above under “Previous Studies and Rationale.” Attendance at *Anza Mapema* support groups and social events by *Shauriana* study participants will be tracked, as will the content of these group and social events during the study period. To ensure fidelity of delivery for each arm, we will review study progress, procedures, and emergent issues at weekly study meetings.

Clinical outcomes that will be tracked by the Anza Mapema Clinic using existing data collection instruments include visit attendance, attendance at clinic-sponsored support groups or social events, diagnosis and treatment of STI, HIV test results, PrEP refills, and PrEP-related adverse events and their management. Treatment will be provided for STI syndromes and acute illnesses as needed. All non-scheduled clinic visits will be documented. The study team (both clinic staff and intervention facilitators) will refer participants who need services beyond their capacity to mental health, substance use, advocacy, and/or legal services provided locally. All referrals will be documented.

Men who discontinue PrEP will continue follow-up; PEP will be available for men reporting high-risk exposure while not taking PrEP. Men who seroconvert will be withdrawn from the study and linked to HIV care at *Anza Mapema* or at another HIV clinic of their choice. As described above under “Recruitment,” participants who withdraw before or test positive at the month 1 visit will be replaced; replacement participants in the RCT will undergo randomization and not necessarily be assigned to the arm to which the participant they replace was assigned.

Intervention delivery. Participants assigned to the *Shauriana* intervention will be introduced to an assigned peer facilitator on the day of their enrolment visit, after which telephone, SMS, and/or WhatsApp contacts from peers will begin, with in-person meetings per the intervention schedule described above. For the RCT, the intervention has been expanded to include an initial introductory session where peer facilitators spend time getting to know their assigned participants. Therefore, five core intervention sessions and an optional additional session will be delivered. All peer facilitator contacts with participants and all required and optional intervention sessions will be documented. RCT participants will be reimbursed 350 KSh for their transportation after receiving each of the five core *Shauriana* modules, as participants may need to travel to a safe space for intervention delivery to ensure privacy.

ACASI measures and data collection. Due to its enhanced privacy, ACASI will be the main method of data collection, in English, Dholuo, or Kiswahili. This method was successfully used in the *Anza Mapema* project. Because participants occasionally have difficulties using ACASI, a research assistant will be available to assist participants if needed. The Anza Mapema clinic has an ACASI in use that includes questions on sociodemographics, sexual history, risk behavior, intimate partner violence, depressive symptoms, alcohol and other substance use, trauma, HIV risk perception, and awareness and use of PrEP and post-exposure prophylaxis for HIV prevention. Data elements that have been added to the ACASI specifically for the *Shauriana* study are listed below in Table 2. Our selection of measures for the *Shauriana* ACASI has drawn from our conceptual model for the *Shikamana* intervention and from the qualitative and intervention development work completed in protocol

MSU/DRPI/MUERC/00637/18. The *Shauriana* ACASI will be updated after the Aim 1 pilot test, balancing the need for data collection with the need to ensure a reasonable ACASI length without undue burden on participants. The final ACASI questionnaire is included in “Appendix F: Shauriana ACASI.”

